#### **L. Sample Size Considerations**

As this is not a powered study but rather a pilot study to evaluate the feasibility of a protocol, no power analysis has been performed. The investigators believe, given their experience with this block in other surgical populations, that a cohort of 10 patients will be satisfactory to assess the primary outcome of 'feasibility.' However, the investigators recognize that the sample size is such that no statistically significant conclusions related to potential benefits may be realizable. Nevertheless, such data should be sufficient to power a more formal study.

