**CHeRP IRB Additional Protocol Information:**

*In addition to the CHeRP SmartForms, all protocols must include the following sections. If a section is not applicable for the current protocol please indicate why this is the case. Please note that a complete protocol\* consists of the CHeRP forms and the information provided in this form.*

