## **E. Definition of Primary and Secondary Outcomes/Endpoints**

### **Feasibility:**

Primary:

- Feasibility: 'Feasibility' will be defined primarily as a successful intervention completion rate of 75% or greater of all subjects with no major adverse outcomes.

Secondary:

- Data integrity: Data integrity will be considered satisfactory if there is successful collection of 75% or greater of all collectible catheter follow-up data points, in aggregate, for successfully completed subjects.
- Efficiency: The treatment will be considered to have an 'efficient intervention duration' if the intervention completion time is found to be less than 40 minutes.

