## **F. Data Collection Methods**

All patients will be assigned a unique personal identifier that will not be linked to any patient identifying information. Data will be collected during the study in case report forms and then will be entered into a password-protected, secure database or automatically collected via the Regional Anesthesia Outcomes Database and uploaded to that same database.

While in the OR, the time required for installing and dressing the catheters, functional assessments, and any complications during placement will be recorded. The surgical procedure and the total surgical time will also be recorded along with any relevant surgical complications.

Each subsequent day of the study (Day 1=24 hours, Day 2 =48 hours), the catheter will be assessed for following adverse events: Presence or absence of catheter dislodgement (catheter out or no longer in a clinically effective position), catheter occlusion, catheter leakage (presence of local anesthetic under occlusive dressing), skin irritation (presence of hyperemic cutaneous reaction not present at dressing placement), and catheter infection (presence of purulent material) by a member of the study team. Intubation status (including extubation time, where indicated), catheter boluses and catheter rate adjustments (if present) will be recorded. Patients' costs and charges will be collected electronically in order understand the healthcare value of this novel pain management strategy

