#### **K. Data Analysis Plan**

At the time of data analysis, datasets will be downloaded from the standard, secure database and merged into Statistical Analysis Systems 9.3 (or more recent) for purposes of analysis. Missing data will be accounted for when the data is coded into respective variables.

Descriptive statistics will be generated in order to summarize demographic characteristics of patients enrolled. Data will be evaluated subsequently with regard to the above-mentioned criteria for 'feasibility.'

Adverse events and complications (if any) associated with the blocks will be recorded and categorized.

Matched groups will be compared for demographic data, Patients costs and charges, risk factors, diagnosis, procedure, and cardiopulmonary bypass and clamp times to ensure their similarities. Once data collection is complete, identifying information will be destroyed.

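### Section K compares costs as a check on matching although Section F collects them as an outcome, and Section L's planning claim rests on no pain or opioid measure named in this form

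*Combined protocol and SAP*

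**What the plan says.** **Costs.** Section F states that patients' "costs and charges will be collected electronically in order understand the healthcare value of this novel pain management strategy". Section K, the analysis plan, then has the matched groups compared on demographic data and on "Patients costs and charges, risk factors, diagnosis, procedure, and cardiopulmonary bypass and clamp times to ensure their similarities". No other use of costs is stated.

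**Planning a later trial.** Section A aims at feasibility and potential benefits for postoperative pain management, ahead of a powered randomized trial. Section L reports that no power analysis was done and grants that, at this sample size, "no statistically significant conclusions related to potential benefits may be realizable". It continues: "Nevertheless, such data should be sufficient to power a more formal study".

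**Measures named.** Section E lists completion without major adverse outcomes, data integrity and intervention duration. Its data-integrity criterion counts "75% or greater of all collectible catheter follow-up data points". Section F lists operating-room and surgical details, catheter events on Days 1 and 2, and costs. It adds: "Intubation status (including extubation time, where indicated), catheter boluses and catheter rate adjustments (if present) will be recorded". Section F also says that data may be "automatically collected via the Regional Anesthesia Outcomes Database", without listing that database's fields. The opening instructions say that a complete protocol "consists of the CHeRP forms and the information provided in this form". Those other forms are not part of the document reviewed.

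**The concern.** There are two linked faults in how the form treats possible benefit.

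(a) A variable used to show that matched groups are alike should not be open to influence by the intervention. Section D(3) places the block after surgery is complete, so part of the cost accrues after the block and may be changed by it. On the wording of Section K, a genuine saving or excess would be read as a sign of poor matching. The question that Section F poses about value would have no analysis of its own.

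(b) In context, the data that Section L calls sufficient are data on potential benefits. The title and Section A make postoperative pain the subject, yet this form names no analgesic measure, time point or analysis. Followed on its own, it does not secure an SD or a between-group difference for any such measure. The formal study could then lack the estimate it was meant to inherit, or take one from a measure chosen after the data were seen.

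**Working it through.** **1. The plan's own figures.** The cohort of 10 comes from no formula. Section L gives no alpha, power, effect or SD, so there is no power figure to reproduce. The matched total in Section H does reproduce: 10 + 2 × 10 = 30.

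**2. Role of cost, section by section.**
- Section F: collected to learn the value of the strategy, which is an outcome purpose.
- Section D(3): the block follows surgery, so later cost is post-intervention.
- Section K: listed beside demographics, diagnosis, procedure, and bypass and clamp times, with similarity as the stated purpose.
- Section E: not listed as an endpoint.

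Bypass and clamp times precede the block and can serve as similarity checks. Total cost cannot, because part of it comes later.

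**3. Search for an analgesic measure.**
- Sections E, F and K: no pain score or postoperative opioid amount.
- Section D(3): rescue opioid is available to all, but no recording of the amount is specified. The medication review after enrollment covers current and past use.
- Section C: opioid consumption and nurse-recorded pain scores appear, but for the earlier retrospective series.
- Section F: extubation time is recorded, and Section B mentions earlier extubation as a possible benefit of regional anesthesia. Section K states no analysis of it.

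**4. Planning precision if a measure is captured.** Assume an approximately normal continuous measure. The 95% limits for the SD, as multiples of the estimate, are sqrt(df/χ²(0.975, df)) and sqrt(df/χ²(0.025, df)). Planned N scales with the SD squared.

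| Patients | df | SD multiplier | N multiplier |
|---|---|---|---|
| 10 pilot | 9 | 0.688 to 1.826 | 0.473 to 3.333 |
| 10 + 20, independent, equal variance | 28 | 0.794 to 1.352 | 0.630 to 1.829 |

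For the pilot alone, 3.333/0.473 is about 7, so planned N spans roughly a sevenfold range. For all 30 patients, 1.829/0.630 is about 2.9.

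Matching weakens the independence assumption. With an assumed within-set correlation of 0.3 or 0.5, the 28 df fall to about 23.7 or 18.6, and the N multiplier becomes 0.61 to 1.93 or 0.58 to 2.10.

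**5. What that means in patients.** Assume two-sided alpha 0.05, 80% power and a standardized difference of 0.5, none of which is in the documents. The nominal size is 63 per arm. Across the 10-patient SD limits it runs from 30 to 210 per arm. For an assumed difference of 1.0, the nominal 16 per arm runs from 8 to 53.

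**The case against.** **The data may exist elsewhere.** The other CHeRP forms, the outcomes database, the medical record (Section G) and the cardiac ERAS program (Section H, with its own IRB number) may all hold pain and opioid data. Section C shows that the hospital has had such data for earlier block patients. This stands. A reader might infer that the pilot will end without analgesic data, above all for the 20 matched patients. The documents do not support that, because those sources were not seen and all 30 patients are in the ERAS program. What remains is that this form neither names the measures, nor says where they are captured, nor states an analysis.

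**Section L is hedged.** It speaks of what should be sufficient, right after admitting the limits of the sample, and no decision in the pilot depends on it. The later trial's endpoint is not stated, and extubation time or cost could inform a trial sized on those. This also stands in part. Analgesia is inferred from the title and aim. The word sufficient is still stronger than the precision allows.

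**The cost point is one compressed sentence.** Section K does plan a between-group cost comparison, and Section F gives its purpose. A reader might infer that a cost difference would lead to re-matching or to dropping patients. Section K sets no balance threshold and attaches no such consequence. The harm is limited to how the comparison would be interpreted.

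**The arithmetic fits any pilot of this size.** True, and it does not show that 10 is wrong for a feasibility aim. It bears only on the claim that the data suffice for planning.

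**Conclusion.** The point holds, at minor severity. The cost part can be shown from the form alone: Sections F and K give the same variable incompatible roles, and the value question is left without an analysis.

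The planning part is narrower. Section L's statement is not supported by what this form names. If the measures are captured elsewhere, planning would still be imprecise: N from 0.47 to 3.33 times the nominal figure using the 10 pilot patients, or 0.63 to 1.83 times using all 30. These ranges assume approximate normality. The second also assumes independent patients and equal variance in blocked and unblocked patients, which the documents do not state.

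A reader might go further and doubt the primary feasibility result. Nothing here touches it: completion and major adverse outcomes depend on neither the cost comparison nor the Section L sentence.

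**What to change.** 1. **Section K, costs.** Take costs and charges out of the similarity list and judge similarity on pre-block variables only. Report costs as an exploratory outcome: the pilot-versus-matched difference with a 95% CI that respects the matching.
2. **Sections E, F and K, analgesic measures.** Name postoperative opioid use and nurse-recorded pain scores over the existing Day 1 and Day 2 follow-up, plus the extubation time already recorded, as exploratory outcomes. Take them from the record for pilot and matched patients over the same window. Report the SD and the between-group difference, each with a 95% CI. If another form or database already captures them, a cross-reference and the analysis wording are enough.
3. **Section L.** Replace the sufficiency sentence with a statement that the data will give imprecise planning estimates, and that the formal study's sample size will be shown across the 95% CI of the SD.

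**Cost of the change.** Chart extraction for 30 patients, less if the data are already held, and edits to the sections above. An extended approval to use the matched patients' data may be needed (an assumption). The Section L statement becomes less favourable. No new patients or procedures are required.

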## **N. Potential Benefits**

There are no known direct benefits to the patients partaking in the study. Currently no data exists to recommend these blocks over conventional management. The results of this study may allow the investigators to develop an appropriately powered, randomized controlled trial to evaluate the utility of this intervention which might be used to inform such management decisions for future patients.

## **O. Privacy Provisions**

Information will only be made available to individuals who are part of the research team. Any results from tests performed for research purposes will not be placed in the medical record. Medical information collected for this study will only become part of your child's medical record if the information is determined to be pertinent to the care your child receives at Children's Hospital Boston. Disclosure of personal information may occur only when required by law.

## **P. Confidentiality Provisions**

All identifying information such as dates of birth, names, and medical record numbers will be removed from the study database. All patients will be assigned to an ID number that will not be linked to any patient identifying information. Data collected for research purposes will not be entered into patient's medical record. All data will be electronically secured in a password protected private folder. Only research investigators and personnel affiliated with the study will have access to patient information.

Every effort will be made by research staff to keep patient information confidential. To ensure patient confidentiality, all research data will be secured in locked filing cabinets in a locked office. Any publications that result from this study will not be linked with personal identifiable information that would disclose the identity of study subjects.

